8.0 Handling of Potential Intercurrent Events for the Primary and Key Secondary Endpoints

Potential intercurrent events considered in the Study M20-371 include 1) premature discontinuation of study drug and 2) CD-related confounding medications defined in Section 8.1. As suggested by Qu et al. (2021), a mix of strategies will be used to handle different intercurrent events for the efficacy analysis.

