2 INTRODUCTION

2.1 Background and Rationale

Why Is This Study Being Conducted?

There are a number of anti-inflammatory biologic therapies available to treat patients with Crohn's disease (CD), including infliximab, adalimumab, certolizumab pegol, vedolizumab, natalizumab, and ustekinumab. In particular, the efficacy and safety of anti-tumor necrosis factor (anti-TNF) monoclonal antibodies, including adalimumab, in CD is well established.^{1,2,3} Adalimumab demonstrated superior efficacy for inducing and maintaining clinical remission compared to placebo in moderate to severe CD patients who failed conventional therapies and infliximab.^{4,5} However, while the available biologic treatments have provided therapeutic options for CD patients, there remain high treatment failure rates associated with existing agents.⁶ Patients with CD treated with anti-TNF agents do not respond at rates of 10% to 40% to initial treatment (primary nonresponse) and additional subjects are observed to lose response over time (secondary loss of response).⁷ Similar patterns of primary nonresponse and secondary loss of response have been observed with other classes of anti-inflammatory biologics used to treat CD.^{8,9} Despite the availability of multiple advanced therapies for the treatment of CD patients, the overall burden of surgery remains high in this population at 3.8 intestinal resections per 100 person-years. Therefore, a large unmet need remains for the treatment of CD.¹⁰

Glucocorticoids have been shown to be efficacious for inducing clinical remission in CD. While nontargeted glucocorticoids with systemic exposure and limited systemic exposure have not been shown to be effective for maintenance treatment,¹¹ approximately 25% of CD patients are glucocorticoid-dependent receiving chronic or recurrent systemic glucocorticoids.^{12,13,14,15} However, the administration of glucocorticoids is limited due to their long-term side effect profile including (but not limited to) hypothalamic-pituitary-adrenal axis (HPA) suppression, osteoporosis, hyperglycemia, glaucoma, and skin atrophy.¹⁶ Thus, the full efficacy of glucocorticoid therapy is often limited with existing agents due to systemic side effects.

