- ✓ 8. Subject must not have evidence of current fistulizing disease, abscess (abdominal or perianal), symptomatic bowel strictures, fulminant colitis, toxic megacolon, or any other manifestation of CD that might require surgery while enrolled in the study.
- ✓ 9. Subject must not have ostomy or ileoanal pouch.
- ✓ 10. Subject must not have a diagnosis of short gut or short bowel syndrome.
- ✓ 11. Subject must not have a history of surgical bowel resection within the past 3 months prior to Baseline, history of $>$ 3 bowel resections due to progression of CD (note: ostomy reversal and hernia repair are not considered related to progression of CD), or $>$ 2 missing segments of the following 5 segments: terminal ileum, right colon, transverse colon, sigmoid and left colon, and rectum.

Subject History

- ✓ 12. Subject must have demonstrated intolerance or inadequate response to one or more of the following biologic agents as defined below. Subjects who discontinued biologic agents only for reasons other than inadequate response or intolerance (e.g., change of insurance) are not eligible to enroll. Subjects with prior intolerance to adalimumab are not eligible to enroll. Where mandated by local requirements: subjects with prior exposure to adalimumab must not have evidence of anti-adalimumab antibodies prior to Baseline.
 - Demonstration of intolerance requires no minimum dose or duration of use.
 - Inadequate response defined as signs and symptoms of persistently active disease (in the opinion of the Investigator) despite a history of one or more of the following:
 - At least one 6-week induction regimen of infliximab (\geq 5 mg/kg IV at Weeks 0, 2, and 6);

- At least one 4-week induction regimen of adalimumab (one 160 mg SC dose at Week 0, followed by one 80 mg SC dose at Week 2 [or one 80 mg SC dose at Week 0, followed by one 40 mg SC dose at Week 2, in countries where this dosing regimen is approved]);
 - At least one 4-week induction regimen of certolizumab pegol (400 mg SC at Weeks 0, 2, and 4);
 - At least one 6-week induction regimen of vedolizumab (300 mg IV at Weeks 0, 2, and 6);
 - At least one 12-week induction regimen of natalizumab (300 mg IV every 4 weeks);
 - At least one 8-week induction regimen of ustekinumab (260 mg [≤ 55 kg] or 390 mg [> 55 to ≤ 85 kg] or 520 mg [> 85 kg] IV, followed by 90 mg SC at Week 8);
 - At least one 8-week induction regimen of risankizumab (600 mg IV at Weeks 0, 4, and 8);

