6.2 Toxicity Management

For subjects who discontinue study drug but continue study participation and are on standard of care therapies, these toxicity management requirements do not apply (including alerts from the central laboratory) and any intolerability to standard of care therapies should be managed by the prescribing physician.

Elective surgery is not allowed during the Induction and Re-Induction Periods of the study. If the subject undergoes elective surgery, study drug should be interrupted at least 2 weeks prior to the planned surgery. If the subject must undergo emergency surgery, the study drug should be interrupted at the time of the surgery. After surgery, allow reintroduction of study drug once the physician has examined the surgical site and determined that it has healed and there is no sign of infection.

Management of Hypersensitivity and Serious Allergic Reactions

Subjects should be closely monitored and assessed for the development of signs and symptoms of hypersensitivity reactions, including anaphylaxis. For any hypersensitivity reaction, appropriate therapy should be instituted per standard of care. Study drug should be discontinued if a subject develops anaphylaxis.

Emergency medical equipment and personnel trained to evaluate and manage infusion-related reactions and anaphylaxis should be immediately available during dosing and the post-treatment observational period.

In the event of a suspected systemic postdose hypersensitivity reaction, if the clinical situation allows, every effort should be made to obtain a serum sample within 2 hours but no later than 6 hours from symptom onset for additional blood tests specified in the Operations Manual, Section 3.19 Hypersensitivity Testing.

IV infusion of study drug for loading dose: The following infusion times should be applied dependent on the subject's individual body weight:

Subject's Body Weight	Infusion Time
≥ 54 kg	60 min
44 to 53 kg	75 min
36 to 43 kg	90 min
27 to 35 kg	120 min

Subjects should be closely monitored for signs and symptoms of hypersensitivity reactions, including anaphylaxis.

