7.10 Sample Size Determination

Approximately 265 subjects will be randomized into 4 ABBV-154 treatment groups or placebo in a 1:1:1:1:1 ratio at Baseline of the Induction Period. There will be a cap of approximately 30% the total enrolled of subjects who had prior use of adalimumab treatment.

A total of 265 subjects (53 subjects per group) will provide more than 90% power to detect a 26% difference in endoscopic response rates at Week 12 of the Induction Period between an ABBV-154 group and the placebo group (assuming the response rate in the placebo group is 11%) using a Chi-square test at α level of 0.1 (two-sided).

Under the response rate assumptions for ABBV-154 and placebo in the Induction Period, it is expected that at least 40 subjects per group will be available for the analysis of endoscopic response at Week 40 in the Maintenance Period. This sample size (40 subjects per group) will provide more than 80% power to detect a 26% difference between ABBV-154 and placebo (assuming the response rate in the placebo group at Week 40 of the Maintenance Period is 11%) using a Chi-square test at α level of 0.1 (two-sided).

The total sample size (planned as 265 subjects) for the Induction Period may be adjusted to ensure at least 40 subjects per group for the analysis in the Maintenance Period.

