Appendix C. Simple Endoscopic Score – CD (SES-CD)

SES-CD is calculated based the sum of individual segment values for four endoscopic variables (presence and size of ulcers, ulcerated surface, affected surface and presence of narrowing). Each variable in each segment be scored 0 to 3 resulting in SES-CD values ranging from 0 to 56 with higher scores indicating more severe disease.

[figure not shown]
SES-CD Scoring:

	Rectum	Sigmoid and Left Colon	Transverse Colon	Right Colon	Ileum	Total
Size of Ulcers Enter: 0 if none 1 if aphthous ulcers (0.1 to ≤ 0.5 cm) 2 if large ulcers (> 0.5 to 2 cm) 3 if very large ulcers (> 2 cm)						
Ulcerated Surface Enter: 0 if none 1 if < 10% 2 if 10% – 30% 3 if > 30%						
Affected Surface Enter: 0 if unaffected segments 1 if < 50% 2 if 50% – 75% 3 if > 75%						
Presence of Narrowing Enter: 0 if none 1 if single, can be passed 2 if multiple, can be passed 3 if cannot be passed						
					TOTAL =	

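### Crohn's-related bowel surgery after Baseline has no intercurrent-event rule, so a resected subject who resumes study drug could count as an endoscopic responder, chiefly at Week 40

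*SAP*

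**What the plan says.** SAP 8.0 opens: "Potential intercurrent events considered in the Study M20-371 include 1) premature discontinuation of study drug and 2) CD-related confounding medications". SAP 8.1 then defines the medication event. In Induction it covers rescue, new glucocorticoids, a failed taper, and new or increased aminosalicylates or immunomodulators. In Maintenance it covers protocol-defined Rescue Therapy only. SAP 8.2 has an exception for subjects who switch to other Crohn's treatment, but it applies only after study drug discontinuation and its list contains drugs only. SAP Tables 1 and 2 and Protocol 7.3 follow the same pattern.

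Protocol 6.2 does foresee surgery. Elective surgery is barred in Induction and Re-Induction. Emergency surgery leads to interruption of study drug, and then: "After surgery, allow reintroduction of study drug once the physician has examined the surgical site and determined that it has healed". Surgery is not on the list of reasons for mandatory discontinuation in Protocol 5.5.

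On scoring, SAP Appendix C states: "SES-CD is calculated based the sum of individual segment values for four endoscopic variables". It has no rule for a segment that was present at Baseline and has since been removed. Under SAP 3.0, endoscopic response is always measured against the Induction Baseline, at Week 40 as well as at Week 12.

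**The concern.** A bowel resection for Crohn's disease during the trial would ordinarily be read as treatment failure. Under the rules as written, nothing makes such a subject a non-responder. If study drug is resumed and the scheduled endoscopy takes place, an evaluation exists. The non-responder imputation in SAP 9.2.1 acts on missing evaluations and on the listed medication events, so it does not apply. If the diseased segment has gone and contributes nothing to the new total, SES-CD can fall by more than half with no change in the remaining bowel.

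What is at stake is the classification of a few subjects on the Week 40 endoscopic endpoint and, less plausibly, on the primary endpoint at Week 12. A diversion or new ostomy raises a related question for the stool-count components of CDAI and SF/AP. With about 40 subjects per Maintenance group, single subjects are visible in the result, and a decision on how to treat them after unblinding would be post hoc.

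**Working it through.** **1. The plan's own power (Protocol 7.10).** The protocol states: "A total of 265 subjects (53 subjects per group) will provide more than 90% power to detect a 26% difference in endoscopic response rates". The placebo rate is 11%, so the active rate is 37%, with a two-sided chi-square test at 0.10. For Week 40 it assumes the same rates with 40 per group and more than 80% power.

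Power = Φ{[Δ − 1.645·√(2p̄(1−p̄)/n)] / √[(p₀(1−p₀) + p₁(1−p₁))/n]}, with Δ = 0.26 and p̄ = 0.24.

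- n = 53: (0.26 − 0.1365)/0.0790 = 1.56, power 94.1%.
- n = 40: (0.26 − 0.1571)/0.0910 = 1.13, power 87.1%.

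Both stated figures are reproduced.

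**2. How a resection could become a response.** Illustrative subject: Baseline SES-CD 12, of which ileum 7 and colon 5. The ileal disease is resected, the colon is unchanged, and the removed segment is assumed to add 0. The new score is 5 and the decrease is (12 − 5)/12 = 58%, which exceeds 50%. In general this needs a resection that removes more than half of the Baseline score.

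**3. How often.** The only rate in the documents is in Protocol 2.1: "the overall burden of surgery remains high in this population at 3.8 intestinal resections per 100 person-years". It is a background figure, and its use here is an assumption.

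- 40 weeks: 0.038 × (280/365.25) = 2.91%; × 40 = 1.2 per group.
- 12 weeks: 0.038 × (84/365.25) = 0.87%; × 53 = 0.46 per group, or × 265 = 2.3 in all.

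These are expected counts of all resections. Only those without rescue, followed by resumed drug and an in-window endoscopy, and removing more than half of the Baseline score, can be misclassified.

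**4. Effect of one misclassified subject.** A group rate moves by 1/40 = 2.5 points at Week 40 and by 1/53 = 1.9 points at Week 12.

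| One subject in | Week 40 difference (power) | Week 12 difference (power) |
|---|---|---|
| neither arm | 26.0 (87.1%) | 26.0 (94.1%) |
| placebo | 23.5 (78.9%) | 24.1 (89.9%) |
| ABBV-154 | 28.5 | 27.9 |

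Two in the Week 40 placebo group would give 21.0 points and 69.1%, but that exceeds the 1.2 expected even before any of the filters in step 3. Equal numbers in both arms cancel in the difference.

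**The case against.** The strongest reply is that few subjects can reach this state.

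- **Week 12 is a narrow route.** Elective surgery is barred, so it takes an emergency resection, healing and an endoscopy within 12 weeks. Any glucocorticoid started after Baseline already makes the subject a non-responder.
- **Entry criteria lower the risk.** Criterion 8 excludes fistulizing disease, abscess, symptomatic strictures and other manifestations likely to need an operation. The Week 40 population is further limited to subjects who entered Maintenance as responders.
- **Many surgical failures are already caught.** After permanent discontinuation, Protocol 5.6 drops endoscopy from the continued procedures, so the assessment is usually missing and counts as non-response. In Maintenance, a worsening subject who takes ABBV-154 rescue is a non-responder from then on.
- **The scoring of a resected segment is not stated.** SAP Appendix E lists 20 individual SES-CD variables for imputation, so a removed segment might be handled as missing. Instructions may also exist in the Operations Manual, which is not among the documents.

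All of this stands as a limit on size. None of it closes the gap. Rescue is at the investigator's discretion, and the Maintenance medication rule is the narrower of the two. Criterion 11 admits subjects with up to two of five segments missing, which suggests, though it does not say, that totals over the remaining segments are accepted.

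A reader might also infer that the protocol itself regards resection as distorting these scores, because criterion 11 excludes a "history of surgical bowel resection within the past 3 months prior to Baseline". The documents do not say so. The only rationale given, in the Protocol Summary of Changes and for the limit on the number of resections, is limited expected benefit.

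**Conclusion.** The gap holds. Crohn's-related bowel surgery after Baseline has no intercurrent-event rule in either document, and the plan as written could count a resected subject as an endoscopic responder. This is a cheap improvement and does not threaten the trial's main result.

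The expected number is at most about 1.2 per 40 subjects over 40 weeks and 0.5 per 53 over 12 weeks, and probably fewer. This rests on two assumptions: that the background rate applies to this screened population, and that a removed segment adds nothing to SES-CD.

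Three stronger readings are tempting and are not supported. First, that the primary endpoint is materially exposed: the Week 12 route is rare. Second, that the treatment difference is biased toward zero because failing placebo subjects have more surgery: the documents give no surgery rate by arm, and the same error in an ABBV-154 group would inflate the effect. Third, that the rate should be raised for a population that has failed biologics: nothing in the documents gives such a figure, and criterion 8 points the other way.

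**What to change.** In SAP 8.0 and 8.1 and Tables 1 and 2, add Crohn's-related bowel surgery (resection, stricturoplasty, diversion or ostomy) as an intercurrent event in Induction and Maintenance. Use the strategies already in the SAP:

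- **Binary endpoints:** composite, non-responder on and after the surgery date, with the override in 9.2.1 extended to this event.
- **Continuous endpoints:** hypothetical, with data on and after the surgery date not used.

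Add to Appendix C how a segment resected after Baseline is scored. Align Protocol 7.3 at the next amendment; Protocol 8.1 requires ethics approval for amendments, so this need not be a separate one.

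Confirm that the eCRF captures the type and date of surgery. Adverse event reporting may not be enough: Protocol 6.1 does not count some pre-planned procedures as adverse events, and the only supplemental procedure form it names is cardiovascular.

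The cost is SAP wording and possibly one eCRF check. Planned sample size and power are unchanged. The downside is that a few subjects become non-responders, so reported rates may be slightly lower.

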8.1 Intercurrent Event 1 (IE1): CD-Related Confounding Medications

The CD-related confounding medications intercurrent event is defined as follows.

In the Induction Period:

1. Initiation of protocol-defined Rescue Therapy for the Induction Period;
2. Initiation of glucocorticoids after Baseline of the Induction Period;
3. Fail to complete glucocorticoid taper by Week 6 of the Induction Period;
4. Initiation/increasing doses of aminosaliclates or immunomodulators.

In the Maintenance Period:

- Initiation of protocol-defined Rescue Therapy for the Maintenance Period.

Within each period, the time point of the CD-related confounding medications intercurrent event is defined as the date when one of the scenarios above occurs for a subject.

Binary endpoints: A composite strategy will be used in the efficacy analysis: the subject will be considered as non-responders at all visits on/after the CD-related confounding medications intercurrent event.

Continuous endpoints: A hypothetical strategy will be used in the efficacy analysis. Data collected on/after the initiation of CD-related confounding medications will not be used in the analysis. Efficacy analysis will be handled by using corresponding statistical models (e.g., the Mixed-Effect Model Repeated Measurement [MMRM] model).

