Any SARS-CoV-2 vaccine information must be documented on the COVID-19 vaccine electronic case report form (eCRF). Refer to the Operations Manual for instructions on reporting any AEs associated with the COVID-19 vaccine.

Rescue Concomitant Medications/Therapy

Unless qualifying for Rescue Therapy or undergoing mandatory tapering for glucocorticoids as described below, no changes may be made to oral glucocorticoids, aminosaliclates, or immunomodulators during the Induction and Re-Induction Periods, or after Week 28 of the Maintenance Period.

In the Induction Period, starting at or after the completion of the Week 8 Visit and thereafter (Week 8 through Week 12), subjects who demonstrate inadequate response as defined below may receive Rescue Therapy with oral glucocorticoids (≤ 20 mg/day prednisone or equivalent, ≤ 9 mg/day budesonide, or ≤ 5 mg/day beclomethasone). Changes in aminosaliclates, or immunomodulators are not permitted during the Induction Period.

In the Maintenance Period, starting at or after the completion of the Week 4 Visit and thereafter (Week 4 through Week 40), subjects who demonstrate inadequate response as defined below will be eligible to receive rescue therapy with a single dose of ABBV-154 600 mg IV at the respective visit, followed by ABBV-154 230 mg SC after 2 weeks and EOW thereafter.

In the Maintenance Period, subjects who have received rescue therapy with ABBV-154 for at least 4 weeks and who continue to demonstrate inadequate response, as defined below, may receive

additional rescue therapy with oral glucocorticoids (≤ 20 mg/day prednisone or equivalent, ≤ 9 mg/day budesonide, or ≤ 5 mg/day beclomethasone), aminosaliculates, or immunomodulators.

In the Induction Period after the Week 8 Visit and in the Maintenance Period after the Week 4 Visit, inadequate response may also be confirmed at unscheduled visits and visits where collection of CDAI components was not planned.

Rescue Therapy is not permitted in the Re-Induction Period.

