7.3 Handling Potential Intercurrent Events for the Primary and Secondary Endpoints

Primary endpoint/Categorical secondary endpoints in the Induction Period:

- Subjects will be considered as not achieving response after receiving medications that could confound the assessment of efficacy, including protocol-defined Rescue Therapy for the Induction Period, initiating glucocorticoids after Baseline, failing to complete glucocorticoid taper by Week 6, and initiating/increasing doses of aminosalicylates or immunomodulators.
- Available data collected after study drug discontinuation will be used until the initiation of medications that could confound the assessment of efficacy.

Categorical secondary endpoints in the Maintenance Period:

- Subjects will be considered as not achieving response after receiving medications that could confound the assessment of efficacy, including protocol-defined Rescue Therapy for the Maintenance Period.
- Available data collected after study drug discontinuation will be used until the initiation of medications that could confound the assessment of efficacy.

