9.3.2 Primary Analysis of Primary Efficacy Endpoint

The attributes of the estimand corresponding to the primary efficacy endpoint are summarized in [Table 1](#).

The primary endpoint will be analyzed between each ABBV-154 group and placebo group in the Induction Period using the CMH test, stratified by the randomization factors (baseline glucocorticoid use (yes/no); endoscopic disease severity (SES-CD < 15; SES CD \geq 15); inadequate response to adalimumab (yes/no)) based on ITT1 population.

Table 1. Summary of the Estimand Attributes of the Primary Efficacy Endpoint

Estimand Label	Attributes of the Estimand				Statistical Summary
	Treatment	Endpoint	Population	Intercurrent Events	
Primary	Each ABBV-154 group vs. placebo in the Induction Period	Achievement of endoscopic response at Week 12 of the Induction Period	Subjects with moderately to severely active CD who had inadequate response to or were intolerant of prior biologics	IE1: Initiation or dose escalation of CD-related confounding medications IE2: premature discontinuation of study drug All subjects will be considered as non-responders at or after IE1 All data after IE2 will be used until initiation of CD-related medications	Difference in the proportion of subjects achieving endoscopic response

The primary efficacy endpoint will be tested at two-sided significance level of 0.1. A CMH based two-sided 95% CI for the difference between treatment groups will be constructed.

The NRI-C approach for handling missing data will be used for main analysis for the primary endpoint.

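### The Induction confounding-medication definition counts starting glucocorticoids but not raising their dose, so a Baseline user who escalates and is off by Week 6 triggers no item

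*SAP*

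**What the plan says.** SAP 8.1 defines the Induction confounding-medication event (IE1) by four items:

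- Item 1 is protocol-defined rescue.
- Item 2, the general trigger for glucocorticoids, is "Initiation of glucocorticoids after Baseline of the Induction Period".
- Item 3, which concerns subjects who enter the study on them, is "Fail to complete glucocorticoid taper by Week 6 of the Induction Period".
- Item 4, which concerns the other two drug classes, is "Initiation/increasing doses of aminosaliclates or immunomodulators".

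For binary endpoints the consequence is that "the subject will be considered as non-responders at all visits on/after the CD-related confounding medications intercurrent event".

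Protocol 7.3 follows the same pattern. After rescue, its list runs "initiating glucocorticoids after Baseline, failing to complete glucocorticoid taper by Week 6, and initiating/increasing doses of", and the only drugs it then names are the other two classes. A dose increase is therefore mentioned only for those.

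The estimand summaries in SAP Table 1 (primary endpoint) and Table 2 (secondary endpoints) describe the event as "IE1: Initiation or dose escalation of CD-related confounding medications".

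On conduct, Protocol 5.4 says that, apart from rescue and the mandatory taper, "no changes may be made to oral glucocorticoids, aminosaliclates, or immunomodulators during the Induction and Re-Induction Periods". Induction rescue is available only from the Week 8 visit.

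**The concern.** The primary estimand is endoscopic response without medication that could confound efficacy. An unplanned increase in glucocorticoid dose is such a medication change on its face, and the SAP treats the corresponding increase in the other two classes that way. Item 2 covers only a start. A subject who enters on oral glucocorticoids, which eligibility criterion 25 allows, can therefore take a higher-dose course early in Induction and still be scored on the observed Week 12 endoscopy.

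A subject not on glucocorticoids at Baseline who takes a course in the same weeks is a non-responder under item 2. Two programmers, one working from 8.1 and the other from the Table 1 label, could score the same Baseline user differently on the primary endpoint.

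**Working it through.** **Tracing the case.** Take a Baseline oral glucocorticoid user who raises the dose of the same drug in Weeks 0 to 6 and is off it by Week 6.

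| SAP 8.1 item | Triggered? | Reason |
|---|---|---|
| 1. Rescue | No | Not available before the Week 8 visit (Protocol 5.4) |
| 2. Start of glucocorticoids | No | The drug was already in use at Baseline |
| 3. Taper not completed | No | Off by Week 6 |
| 4. Start or increase | No | Covers only aminosalicylates and immunomodulators |

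Neighbouring cases are covered or arguable. Use beyond Week 6 meets item 3. A restart after a completed taper, or a switch to a new agent, can be read as item 2.

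**Whether anything else in the SAP closes the gap.**
- Section 8.2 deals with other CD treatments after study-drug discontinuation and is also worded in terms of initiation.
- Appendix A tabulates prohibited-medication deviations but does not change response status.
- The NRI-NC sensitivity analysis uses the same IE1 definition.
- The as-observed analysis uses all data after IE1, so it does not isolate these subjects.

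**The plan's own figure.** SAP 2.4 gives 53 per group, 11% on placebo, a 26-point difference (so 37% on ABBV-154) and a two-sided chi-square test at 0.1, with power above 90%. By normal approximation:
- pooled rate = (0.11 + 0.37)/2 = 0.24; null SE = √(2 × 0.24 × 0.76 / 53) = 0.0830;
- alternative SE = √((0.11 × 0.89 + 0.37 × 0.63)/53) = 0.0790;
- z = (0.26 − 1.645 × 0.0830)/0.0790 = 1.56, so power is 94.1%.

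The stated figure is reproduced and does not depend on this point.

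**Size.** The documents give neither the share of Baseline users nor the frequency of early increases, so both are assumed here.
- Baseline users per arm at 30%: 0.30 × 53 = 15.9.
- Affected at 5-10% of these: 0.8-1.6 subjects.
- Upper limit if every one responds: 0.8/53 = 1.5 points to 1.6/53 = 3.0 points.
- At the planning response rates: 0.8 × 0.11 = 0.09 to 1.6 × 0.37 = 0.59 responders per arm, or 0.2-1.1 points.

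With wider assumptions (20-40% Baseline users, 5-20% of them affected, 11-37% responding):
- low end: 0.20 × 0.05 × 53 = 0.5 subjects, 0.06 responders, 0.1 points;
- high end: 0.40 × 0.20 × 53 = 4.2 subjects, 1.6 responders, 3.0 points.

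One reclassified responder moves an arm by 1/53 = 1.9 points. If exactly one extra responder fell in placebo and none in the active arm, the same power formula with a placebo rate of 0.11 + 1/53 = 0.129 gives 89.9%. Under the 30% and 5-10% assumptions, the expected number is below one per arm.

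**The case against.** **A reader might infer that Table 1 flatly contradicts 8.1.** That is stronger than the text supports. The tables are headed as summaries, and SAP 8.0 says the confounding medications are defined in 8.1. As a short label for a four-item list, initiation or dose escalation is accurate: items 1, 2 and 4 involve initiation, and item 4 involves escalation. The label also leaves out the failed taper, so it cannot be a full definition. What remains is a label broader than the rule it summarises, and a rule that omits one class without a stated reason.

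**The increase is prohibited anyway.** This is true, but Protocol 5.4 restricts changes in all three classes and item 4 still counts increases in two of them. Prohibition does not explain the omission.

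**The route is narrow.** This stands. The subject must be a Baseline user, depart from Protocol 5.4, still be off by Week 6, and then respond on an endoscopy about six weeks or more after the last dose. The taper schedule is not in the documents available here, so it cannot be checked how often such a course could end by Week 6, or whether an increase would itself count as failing the taper.

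**A reader might infer that one randomisation stratum is let off and the other penalised.** This is only partly so. Baseline users face item 3, which non-users do not. The rule is the same in every arm, and the CMH test is stratified by Baseline glucocorticoid use.

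**Conclusion.** The gap is real and worth closing, as a minor clarification. Read literally, SAP 8.1 and Protocol 7.3 let a prohibited early increase in glucocorticoid dose pass without effect on the primary endpoint, and no other rule or sensitivity analysis corrects this.

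The effect is probably small: about 0.2-1.1 points per arm at the planning response rates, and at most 1.5-3.0 points if every affected subject responds. Both ranges rest on an assumed 30% Baseline use and 5-10% affected, neither of which comes from the documents.

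A reader might also infer that the gap favours placebo, because early worsening should be more common there, and so shrinks the treatment difference. That is conceivable, but the documents give no data on early increases by arm, so the direction of bias is not established.

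**What to change.** Before unblinding, amend SAP 8.1 item 2 and the matching words in Protocol 7.3. IE1 would then include initiation of, or any post-Baseline dose increase of, non-inhaled glucocorticoids, including re-escalation during the taper, dated at the increase. Wording limited to increases above the Baseline dose would miss re-escalation during the taper and would still not match Tables 1 and 2.

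Keep permitted inhaled use outside the event. Protocol 5.4 allows a short-term inhaled increase for an adverse event unrelated to CD and exempts inhaled use from its own non-responder list, whereas SAP 8.1 item 2 does not state that exemption.

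That Protocol 5.4 list, which governs entry to Re-Induction, also refers only to initiating glucocorticoids. It must be reconciled with the amended analysis definition. This point concerns the analysis definition only and takes no position on the treatment-allocation rule.

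The cost is a short text change in the SAP and Protocol 7.3, plus the reconciliation in 5.4. Concomitant medication is already recorded, and item 4 already needs dose-change data. The downside is a few more subjects scored as non-responders and, for continuous endpoints, a few more post-event values set aside under the hypothetical strategy in 8.1.
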